**4. Purpose, hypothesis and key questions:**

The proposed study will examine the threshold for nicotine self-administration (NSA) using five different nicotine doses in young adult male and female non-dependent smokers (light and intermittent smokers or LITS). We propose a double-blind, placebo-controlled study that will enroll 195 individuals, targeting a total of 72 completers (36 male and 36 females). In each of the five experimental sessions, smokers will be randomly assigned to one of the five doses of nicotine (0.0125, 0.025, 0.05, 0.1 and 0.2 mg/70 kg). The highest dose, 0.2 mg/70 kg, corresponds to nicotine delivered by about one or two puffs of a cigarette. At the beginning of each experimental session, smokers will sample the assigned both the nicotine dose for that experimental session, and the placebo (saline) dose, followed by the opportunity to choose between nicotine and placebo for a total of ten choices over a 165-minute period. The main outcomes will be threshold dose (the minimum dose of nicotine that is self-administered more than placebo) and the slope of dose-response for nicotine self-administration (changes in nicotine self-administration per unit change in nicotine dose). We will also collect measures of nicotine intake (cotinine), nicotine clearance (3-hydroxycotinine (3-HC) / cotinine), and self-report drug effects.

The following questions will be addressed:

Aim #1: To assess the threshold reinforcing dose and dose-effect curve for IV NSA at low doses in young adult LITS.

Hypothesis #1A: The threshold reinforcing doses for IV NSA will be between 0.0125 to 0.1 mg/70 kg.

Hypothesis #1B: The dose-effect curve for NSA will differ between males and females with relatively flat curve in female smokers.

Aim #2: To assess the threshold and dose-effect curve for the positive and negative/aversive subjective effects of IV nicotine at low doses and its relationship to nicotine reinforcement.

Hypothesis #2 A: The threshold for the positive effects will be between 0.0125 to 0.1 mg/70 kg, for the negative/aversive effect it will be  $\geq 0.1$  mg/70 kg.

Hypothesis #2B: Nicotine reinforcement will be positively correlated with the positive and negatively correlated with the negative/aversive subjective effects of IV nicotine.

Exploratory Aims: To examine the influence of nicotine clearance rate on nicotine reinforcement threshold and dose-effect curve.

## 5. Background:

### *Addictive threshold for nicotine*

Similar to other drugs of abuse, cigarette smoking is rewarding (e.g., drug liking or good drug effects) and reinforcing (self-administered). Previous studies have shown that smoking a cigarette delivers approximately 1 to 1.5 mg of nicotine, inhaled over 10 to 12 puffs (Benowitz and Jacob 1984). A group of smokers known as light and intermittent smokers (LITS) or 'chippers', show few or no signs of addiction (Shiffman 1989). Based on the nicotine intake of the LITS, it has been suggested that blood cotinine levels over 50 to 70 mg are needed to sustain nicotine addiction in smokers (Benowitz and Henningfield 1994). This threshold roughly corresponds to a daily intake of 5 mg nicotine or approximately smoking 5 cigarettes/day. Based on these figures, Henningfield et al (1998) estimated that the threshold for nicotine reinforcement is approximately 0.2 mg of delivered nicotine. As will be summarized below, this estimated threshold for nicotine reinforcement has yet to be validated by carefully controlled nicotine administration studies.

Since cigarette smoke contains many other compounds in addition to nicotine and the amount of nicotine delivered via smoking cannot be reliably controlled, cigarette smoking is not suitable for examining dose-dependent nicotine effects (Hoffmann and Wynder 1986). Pure nicotine administration studies, especially via nasal spray, have provided crucial information for the threshold doses of nicotine that are reinforcing. Nasal spray provides quicker nicotine delivery, compared to nicotine gum or patch, and the amount of delivered nicotine can be reasonably controlled (Perkins 2009). In a series of studies, Perkins et al. (1994) have shown that smokers and non-smokers can reliably detect the interoceptive stimulus effects of intranasally administered nicotine using the drug discrimination procedure. The threshold for nicotine discrimination is approximately 3 mcg/kg (0.21 mg for a 70 kg individual) for smokers and 2 mcg/kg (0.14 mg for a 70 kg individual) for nonsmokers (Perkins et al. 2001). The threshold doses for nicotine discrimination are likely lower than the reinforcement threshold since smokers are unlikely to find nicotine reinforcing if the dose is below that for which they can detect its subjective effects (Perkins 2009). Importantly, smokers did not self-administer nicotine nasal spray doses, which were either above or below the threshold for nicotine discrimination, more than placebo (6.1 and 7.4, out of 16 choices) (Perkins et al. 2001). This lack of reinforcement might be due to the slower rate of nicotine delivery via spray, which does not match the rapid nicotine delivery via smoking. Thus, although the nicotine discrimination studies with nasal spray provide crucial information for the threshold of the interoceptive stimulus of nicotine, the threshold for nicotine reinforcement remains to be determined using more rapid delivery systems.

### *Dose-response curve for nicotine reinforcement*

Characterization of the dose-response curve of a drug provides crucial information including the minimum effective or threshold dose as well as the shape and slope of the dose-response curve. While the shape of the dose-response curve indicates how the response changes at different dose levels (e.g., linear, U-shaped, or flat), a higher slope indicates greater response to dose increases (i.e., greater sensitivity). The dose-response curve for IV nicotine self-administration has been well characterized in preclinical studies (Corrigall et al. 2000; Donny et al. 2000; Fattore et al. 2002; Le Foll et al. 2007; Rose and Corrigall 1997). The typical pattern of nicotine self-administration behavior that has emerged from many preclinical studies is that the dose-dependent changes in drug use behavior are restricted to low and high dose ends of the dose-response curve, while the middle range is relatively insensitive to changes in nicotine doses (Rose and Corrigall 1997). Consistent with these findings, in our previous study with IV nicotine self-administration, we observed no change in nicotine self-administration between 0.4 and 0.7 mg of nicotine (Sofuođlu et al. 2008a). A similar insensitivity of smoking behavior has been observed when nicotine intake is experimentally manipulated (Benowitz and Jacob 1990).

Further characterization of the dose-response curve for nicotine reinforcement remains to be examined using rapid and accurate nicotine delivery systems.

#### *IV nicotine administration*

We propose to use IV NSA to determine the threshold for nicotine reinforcement due to its advantages over other routes of pure nicotine. First, the IV route produces fast nicotine delivery with peak plasma levels reached in 20 sec, which is comparable to smoking (Rose et al. 2003; Zins et al. 1997). Second, IV nicotine provides accurate dosing by delivering nicotine directly into the circulation and bypassing the absorption step, which shows significant individual variation. Third, IV nicotine is reinforcing in rodents, primates, and humans. Rats and monkeys self-administer IV nicotine (Corrigall et al. 2000; Donny et al. 2000; Fattore et al. 2002; Le Foll et al. 2007; Rose and Corrigall 1997). In humans, when administered rapidly (i.e., in less than 60 sec), IV nicotine elicits pleasurable subjective effects such as “good effects” and “drug liking” similar to those elicited by smoking and is self-administered by smokers (Harvey et al. 2004; Henningfield and Goldberg 1983; Henningfield et al. 1983). Thus, the rapid and accurate dose delivery, combined with reinforcing effects, makes IV nicotine an optimum route to examine the threshold for nicotine reinforcement.

A critical issue in IV NSA studies is the dose of nicotine. In the Harvey et al (2004) study, male smokers preferred nicotine injections over saline-administration for 0.75, 1.5, or 3.0 mg/injection of nicotine doses. These nicotine doses, however, are much higher than the typical nicotine intake of an average smoker, which is 1-4 mg nicotine/hour (Benowitz and Jacob 1990). To address this limitation, in a recent study, we examined self-administration of nicotine doses within the range of average intake by smokers (Sofuoglu et al. 2008a). We used a choice procedure in which male and female smokers were able to choose between various IV nicotine doses (0.1, 0.4, and 0.7 mg) or saline. Both the 0.4 and 0.7 mg/70 kg, but not the 0.1 mg, doses were preferred over placebo. In a more recent study, we examined self-administration of lower doses of nicotine (0.1, 0.2, 0.3 or 0.4 mg) using a more rapid, 30 sec, delivery rate 12 male and 14 female smokers (34). NSA was negatively correlated with nicotine dose in males who displayed choice preference for lower doses (0.1 and 0.2 mg doses) of nicotine over the highest tested dose (0.4 mg). However, no significant relationship between dose and choice preference was evident in females. The 0.1 and 0.2 mg nicotine doses also produced positive subjective effects, suggesting that nicotine reinforcement threshold is equal or less than 0.1 mg. To our knowledge, the dose-effect curve of nicotine in doses less than 0.1 mg has not been examined in humans.

#### *Proposed Study*

Although the presumption of an addictive threshold dose of nicotine is one of the pillars of nicotine reduction strategies, it has yet to be characterized in well-designed human studies. This project will address this gap by assessing the threshold and dose-effect curve for NSA over a low dose range that is expected to capture the reinforcement threshold. It is likely that the nicotine reinforcement threshold will display inter-individual differences. Older and dependent smokers, compared to young adult LITS, may likely have higher reinforcement threshold due to tolerance to nicotine's behavioral effects as a result of long-term nicotine intake. We chose young adult LITS given that the threshold for addictive doses of nicotine was estimated based on the nicotine intake of LITS. As suggested by previous findings from our, and other research groups, male and female smokers may differ in their sensitivity to the behavioral effects of nicotine. In addition, there is evidence to suggest that the rate of nicotine clearance may affect nicotine dose-effect curve and reinforcement threshold. Therefore, the influences of both gender and nicotine clearance rate [assessed by the ratio of hydroxycotinine/cotinine or otherwise known as the nicotine metabolite ratio (NMR)] will be examined in this application. This project will also examine the relationship between NSA and the positive and negative/aversive subjective effects of IV nicotine.

These subjective measures are important because evidence suggests that while positive drug effects are associated with abuse liability and drug intake, sensitivity to the negative/aversive subjective effects of nicotine may prevent both the initiation of tobacco product use and the amount of nicotine intake in established tobacco users. Accordingly, nicotine reinforcement may be a function of the relative balance between nicotine's positive and negative/aversive effects. However, to what extent the individual's sensitivity to the negative/aversive effects of nicotine changes the threshold and dose-effect function for nicotine reinforcement has not been determined. Identifying factors that affect the reinforcement threshold of nicotine will be an important step in developing science-based policies for reducing nicotine in tobacco products.

### Preliminary Studies

#### Study 1: Sex differences in nicotine self-administration of low doses of nicotine in smokers.

**Aim:** The goal of this study was to investigate the dose-response function for the reinforcing and subjective effects of intravenous (IV) nicotine in male and female smokers using nicotine doses that are estimated to be delivered by smoking one or two puffs of cigarettes.

**Method:** Twenty-six smokers (12 male and 14 female) participated in a double-blind, placebo-controlled, crossover study that included 4 experimental sessions. In each session, participants were randomly assigned to one of 4 doses of nicotine (0.1, 0.2, 0.3 or 0.4 mg). In each session, subjects first received the sample infusions of the assigned nicotine dose and placebo and then had the opportunity to choose between nicotine and placebo for a total of 6 choices spaced evenly over a 90-minute period. The main outcome measures were the number of nicotine choices, self-report drug effects and physiological responses. **Results:** A sex-by-dose interaction was observed in the nicotine choice paradigm (Fig 1). Nicotine self-administration rate was negatively correlated with nicotine dose in males (males displayed choice preference for low doses of nicotine over high doses of nicotine), but no significant relationship between dose and choice preference was evident in females. Overall, the number of nicotine choices was not greater than saline choices ( $p>0.05$ ).

[figure not shown]
[figure not shown]

Figure 1. The mean ( $\pm$  SEM) nicotine infusion number (maximum 6) for male (n=12) and female (n=14) subjects at each dose is shown. Nicotine self-administration frequency was negatively correlated with nicotine dose among males but not females (dose by sex  $p < 0.05$ ). Post hoc comparisons showed that both 0.1 and 0.2 mg doses were self-administered more than the 0.4 mg nicotine doses.

(0.1, 0.2, 0.3, 0.4 mg) were rated as more pleasurable than saline (Figure 2). The aversive effects were significantly higher relative to saline in response to nicotine at 0.3 mg, but not at the other nicotine doses.

**Conclusions:** Among males, low doses of IV nicotine were preferentially chosen over high doses of nicotine. In contrast, among females no dose-sensitive choice preference was observed. The IV nicotine doses also induced subjective ratings of positive and negative drug effects that differed from saline. Notably, all doses tested, including the lowest tested dose (0.1 mg) were rated as more pleasurable than saline by both sexes, indicating abuse potential for all tested doses, although the number of nicotine choices were not greater than those for saline. This discrepancy could be due to the small sample size and the relatively few opportunities to self-administer nicotine at each dose (up to 6 choice trials per dose). These limitations will be addressed in the current study.

The dose-dependent sex differences in reinforcement behavior and the dose-dependent changes in positive and negative subjective ratings of drug effects are relevant to dependence vulnerability. These findings, which demonstrate sex differences in NSA for doses that are near to the reinforcement threshold, suggest that male and female smokers may respond differently to changes in nicotine doses available for self-administration. The negative correlation between nicotine dose and self-administration suggests partial compensation in males.

**Study 2: Higher 3-hydroxycotinine (3-HC)/cotinine is associated with greater reward and heart rate increases from intravenous nicotine:** In previous studies, high nicotine metabolite ratio (3-HC/cotinine) predicted poor outcomes for smoking cessation treatment with nicotine patch. The underlying mechanisms that associate metabolite ratio with treatment outcomes have not been fully elucidated. A total of 100 smokers were divided into quartiles based on their baseline plasma nicotine metabolite ratio. Following overnight abstinence, smokers received saline followed by escalating intravenous doses of nicotine (7 and 14 mcg/kg) given 30 min apart. Smokers in the first quartile (slower metabolizers) had lower FTND scores, suggesting lower levels of dependence. In contrast, smokers in the fourth quartile (faster metabolizers) reported greater craving for cigarettes following overnight abstinence from smoking and reported greater ratings of nicotine-induced good drug effects, drug liking, and wanting more drug. Higher nicotine metabolite ratio was also associated with greater heart rate increases in response to nicotine. These results suggest that nicotine metabolite ratio may influence the subjective rewarding and physiological effects from nicotine and withdrawal severity.

**Figure 2. Subjective ratings of the pleasurable and aversive effects of intravenous nicotine in smokers.** Shown is the mean value ( $\pm$  SEM) for 6 post-infusion ratings of drug effects for subjects ( $n=26$ ). The subjective ratings for nicotine are relative to the ratings for saline, using the DEQ with a scale of 0-10.

Further, all nicotine doses

In summary, our previous work demonstrates the feasibility of IV nicotine self-administration to determine the reinforcement threshold for nicotine in LITS. Our findings point to a range of nicotine doses, 1.5 to 6.0 mcg/kg, that is well-tolerated by non-dependent smokers and can be used to determine the reinforcement threshold. Our group has unique expertise and a track record in conducting IV nicotine administration studies in both male and female smokers.

## **6. Significance:**

The proposed study is highly significant. First, this study will be especially informative in determining the threshold doses of nicotine needed to maintain nicotine self-administration in male and female LITS smokers. Characterization of the shape and slope of dose-response curves for the reinforcing effects of IV nicotine will help to accurately determine how male and female smokers adapt their nicotine self-administration to reductions in nicotine doses that are available. Whereas the actual threshold and dose-response function may differ in cigarette smoke-delivered nicotine, the IV self-administration data should contribute to a better understanding of the potential threshold and dose-response function for nicotine reinforcement in general. Second, the proposed study will likely foster further preclinical and clinical research on nicotine reinforcement and its moderation by sex. Since the IV route is commonly used for nicotine self-administration studies in rodents and primates (Le Foll et al. 2007), findings from our study will allow translational comparisons of threshold and dose-response curves for nicotine reinforcement between human and animal studies. Finally, the goals of this proposal are also highly relevant to the FDA's new mission of setting standards for the evaluation of new tobacco products as well as the risks of initiation and dependence and consistent with the recommendations of the World Health Organization (WHO) for further evaluation of the importance of nicotine in the appeal, addiction potential, and harmful effects of cigarette smoking (WHO, 2007). Ultimately, the result of this study may provide information that is crucial for the development of science-based policies to control the addictive potential of cigarette smoking for both male and female smokers.

## **7. Subjects:**

Inclusion criteria: 1) Female and male smokers, aged 18 to 35 years, who have been smoking for at least a year, and a life-time consumption of at least 100 cigarettes; 2) smoke more frequently than once a week and  $\leq 5$  cpd; 3) FTND score  $\leq 3$  indicating no or minimal evidence for nicotine dependence; 4) urine semi-quantitative cotinine levels  $> 100$  ng/mL indicating an active smoking status; 5) not seeking treatment at the time of the study for nicotine dependence; 6) in good health as verified by medical history, screening examination, and screening laboratory tests; 7) for women, not pregnant as determined by pregnancy screening, nor breast feeding, and using acceptable birth control methods.

Exclusion criteria: 1) history of major medical illnesses that the physician investigator deems as contraindicated for the subject to be in the study; 2) requirement of any form of regular psychotropic medication (antidepressants, antipsychotics, or anxiolytics) or psychiatric diagnosis and treatment for psychiatric disorders including major depression, bipolar disorder, schizophrenia in the past 6 months; and 3) current dependence to alcohol or any other recreational or prescription drugs and; 4) daily use of smokeless tobacco products or exclusive daily use of e-cigarettes (non-daily users will be included).

Justification for age criteria: The study will enroll young adults between the ages of 18 to 35 because this age group represents a critical time for development of nicotine addiction, with almost all progression to daily smoking completed by the age of 26.

Stratified sampling procedure for race and presence of daily smoking: The study will enroll 36 male and 36 female LITS. The two groups will be matched on race and presence of daily smoking. Race has been shown to influence smoking behavior and nicotine pharmacokinetics. We will create a race variable (0= Caucasian, 1= African-American, 2=Other) to match groups on race. We will also stratify for the presence of daily smoking because daily smoking may influence the behavioral effects from smoking by tolerance development (9-11). This approach will allow balancing the male and female smokers for light vs. intermittent smokers. A categorical variable will be created for the presence of daily smoking (1= present, and 0 = absent).

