## **E. Study Procedures**

**Session procedures:** Before the test sessions, smokers will be required to abstain from smoking for 10 h, which will be verified by expired air CO levels  $\leq 8$  ppm (Benowitz et al. 2002). Subjects will be asked to refrain from consuming alcoholic beverages and drugs during study participation, which will be verified by a urine drug quick test. If results indicate non-compliance with these study procedures, subjects will be discharged from the study. Subjects will be instructed to drink their typical amount of caffeinated beverages in the morning to minimize caffeine withdrawal, which could confound the study measures. Subjects will be instructed not to eat for four hours before the lab sessions to reduce the chance of vomiting. A light lunch will be provided at the end of each experimental session.

**Medical monitoring:** Subjects will be given a thorough physical examination prior to entry in the study. For nicotine administration sessions, a physician will be present and subjects will be attached to a cardiac monitor as well as a blood pressure and heart rate monitoring device. An IV catheter will be in place throughout the session. Subjects will be administered nicotine only if the systolic blood pressure is  $<150$  mmHg and heart rate is  $<100$  beats/minute. Subjects will be terminated from the study if the blood pressure at any time is  $>170/110$  mm Hg, the heart rate is  $>120$  beats/min, or if they develop signs and symptoms compatible with nicotine toxicity. Subjects will remain in the laboratory for at least an hour after the last nicotine administration. These procedures have been developed as part of our IND for IV nicotine.

TABLE 1. SCHEDULE OF EVENTS: EXPERIMENTAL SESSION\*

Minutes	Time point	Measures and Events
0 Min	1	HR/BP, DEQ, IV nicotine or saline administration A (sampling) CO, HR/BP, EKG, M
1 Min	2	HR/BP, DEQ
2 Min	3	HR/BP,
3 Min	4	HR/BP, DEQ
5 Min	5	HR/BP, DEQ
15 Min	6	HR/BP, DEQ IV nicotine or saline administration B
16 Min	7	HR/BP, DEQ
17 Min	8	HR/BP
18 Min	9	HR/BP, DEQ
20 Min	10	HR/BP, DEQ
30 Min	11	HR/BP, DEQ IV Choice Sampling Option 1
31 Min	12	HR/BP, DEQ
32 Min	13	HR/BP
33 Min	14	HR/BP, DEQ
35 Min	15	HR/BP, DEQ
45 Min	16	HR/BP, DEQ IV Choice Sampling Option 2
46 Min	17	HR/BP, DEQ
47 Min	18	HR/BP
48 Min	19	HR/BP, DEQ
50 Min	20	HR/BP, DEQ
60 Min	21	HR/BP DEQ IV sampling Option 3
61 Min	22	HR/BP, DEQ
62 Min	23	HR/BP
63 Min	24	HR/BP, DEQ
65 Min	25	HR/BP, DEQ

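### The e-cigarette exclusion leaves at least some daily vapers eligible, apparently against its own parenthesis, and the pre-session abstinence rule does not cover vaping

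*Combined protocol and SAP*

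**What the plan says.** All eligibility rules are in Section 7 of the combined protocol and SAP.

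- Inclusion 1 takes smokers "who have been smoking for at least a year, and a life-time consumption of at least 100 cigarettes".
- Inclusion 2 requires that they "smoke more frequently than once a week and" at most 5 cigarettes per day (cpd).
- Inclusion 3 requires an FTND score of 3 or less, "indicating no or minimal evidence for nicotine dependence".
- Inclusion 4 requires urine cotinine above 100 ng/mL, "indicating an active smoking status".
- Exclusion 3 bars "current dependence to alcohol or any other recreational or prescription drugs". It does not name nicotine.
- Exclusion 4 bars "daily use of smokeless tobacco products or exclusive daily use of e-cigarettes (non-daily users will be included".

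The two sex groups are matched on race and on a yes/no variable for daily smoking. The reason given for the second is that daily smoking may produce tolerance. There is no corresponding variable for e-cigarettes.

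Section 11.E states that "smokers will be required to abstain from smoking for 10 h, which will be verified by expired air CO levels" of 8 ppm or less. Section 11.A explains overnight abstinence as a control for recent nicotine intake. Section 11.C (Biochemical) adds a plasma nicotine measurement before each session to confirm overnight abstinence from smoking, without a cut-off or a consequence.

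**The concern.** Exclusion 4 treats two non-cigarette products differently without giving a reason. Daily smokeless use disqualifies outright, but daily e-cigarette use disqualifies only when it is exclusive. In a study whose subjects must all smoke cigarettes, that qualifier removes much or all of the clause's effect. The parenthesis suggests that the authors meant to admit only occasional users, so two screeners could reasonably decide differently on the same candidate.

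The protocol's own reasoning makes this relevant. Section 5 (Proposed Study) says that older and dependent smokers "may likely have higher reinforcement threshold due to tolerance to nicotine's behavioral effects as a result of long-term nicotine intake", and the matching on daily smoking has a similar rationale. Daily vaping is a source of nicotine that the cpd limit does not count and the matching variable does not record. If it matters, it bears on the threshold dose and the slope (the two main outcomes), and on the male-female comparison in Hypothesis 1B if dual use differs between the sexes.

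The abstinence rule is a second and separate gap. E-cigarette users are expressly admitted, yet the session instruction restricts smoking only. Carbon monoxide comes from combustion, so a low reading does not show that the subject has not vaped.

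**Working it through.** The plan gives no figure on this point, so the check is a logical one. Take candidates who meet every other criterion, including FTND of 3 or less and cotinine above 100 ng/mL, and apply inclusion 2 and exclusion 4. Reading A takes 'exclusive' to mean that the person uses e-cigarettes and no cigarettes. Reading B takes it to mean that e-cigarettes are the only product used daily.

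| Candidate | Inclusion 2 | Exclusion 4, reading A | Exclusion 4, reading B |
|---|---|---|---|
| Vapes daily, smokes no cigarettes | fails | already out | already out |
| Vapes daily, smokes twice a week | passes | eligible | excluded |
| Vapes daily, smokes daily up to 5 cpd | passes | eligible | eligible |
| Vapes less than daily, smokes up to 5 cpd | passes | eligible | eligible |
| Uses smokeless tobacco daily, smokes up to 5 cpd | passes | excluded | excluded |

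The third row settles the point, because that candidate is eligible on both readings. The second row is where the readings part. Under A the e-cigarette clause adds nothing to inclusion 2. Under B it removes the intermittent smokers who vape daily.

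Next, see whether another rule stops the candidate in the third row.

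- The cpd limit counts cigarettes.
- FTND of 3 or less must be met and may exclude some. Section 11.C lists no separate measure of e-cigarette dependence.
- The cotinine rule is a floor with no ceiling, so nicotine from vaping can only help a candidate to pass.
- Exclusion 3 does not mention nicotine.
- The daily-smoking variable codes this candidate 1 because of the cigarettes and does not register the vaping. Under reading A, the candidate in the second row is coded 0.

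For the sessions, compare three statements. Section 11.A gives the purpose as control of recent nicotine intake. Section 11.E gives the rule as 10 h without smoking, checked by carbon monoxide. Section 11.C adds plasma nicotine, which can reflect nicotine from any product. The rule is narrower than the purpose. The measurement that could close the gap has no threshold, no stated time by which the result is known, and no consequence.

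For size, the documents give no share of daily dual users. Purely as an assumption, shares of 5%, 10% and 20% of the 72 planned completers would be 0.05 × 72 = 3.6, 0.10 × 72 = 7.2 and 0.20 × 72 = 14.4, or about 4, 7 and 14 people. These are head counts only and say nothing about the direction or size of any bias.

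**The case against.** The strongest reply is that this is an ambiguity of wording and that the plan has more protection than it first appears. Several parts of that reply stand.

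- A reader might infer that the e-cigarette clause can never exclude anyone. That holds only under reading A. Reading B gives the clause some effect and is at least arguable.
- A reader might infer that the plan states that only non-daily users may enter. The parenthesis does not contain the word 'only'. The conflict with 'exclusive' is an implication, though a natural one.
- A reader might infer that vaping on the morning of a session would go undetected. Plasma nicotine is taken before each session, so it could be seen. What is missing is a rule that acts on it.
- A reader might infer that daily nicotine users fall outside the intended population. Section 7 deliberately admits daily smokers of up to 5 cpd and balances the sexes on daily smoking. The concern can only be additional intake, or dependence, from vaping.
- A reader might infer that admitting daily vapers raises the threshold, flattens the curve or biases the sex contrast. Section 5 says only that a higher threshold is likely in older and dependent smokers, and it does not say that tolerance flattens the curve. None of these effects is shown.

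Admitting dual users could also be a legitimate choice in favour of a broader population. If so, the plan should say so and account for it, and it currently does neither. The reply does not remove the third row of the table, the unequal treatment of smokeless tobacco and e-cigarettes, or the mismatch between the purpose of abstinence and its rule.

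**Conclusion.** The point holds in a limited form. As written, exclusion 4 leaves eligible at least those who both smoke (up to 5 cpd) and vape every day with FTND of 3 or less. This sits uneasily with its own parenthesis. No upper cotinine limit, matching variable or listed analysis accounts for them. The abstinence rule covers smoking only, although its stated purpose is to control recent nicotine intake, and the plasma nicotine that could enforce that purpose has no decision rule.

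These conclusions follow from the text and do not depend on how 'exclusive' is read. The documents show who is eligible, not who was enrolled. The number of daily dual users and any effect on threshold, slope or sex contrast are unknown. The sample size rationale in Section 12 does not depend on this point. The case for change is that the gap is certain and cheap to close, not that harm has been demonstrated.

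**What to change.** 1. Reconcile 'exclusive' with the parenthesis in exclusion 4. The simplest way is to delete 'exclusive', so that daily e-cigarette use is handled like daily smokeless use. If daily dual users are wanted, say so and stratify or adjust for them.
2. Extend the 10 h abstinence instruction to all nicotine products.
3. Set in advance a plasma nicotine cut-off, and use the samples already planned to flag sessions with recent intake for the analysis.
4. Record e-cigarette use (product and frequency) for every subject, including those already enrolled.
5. Repeat the Aim 1 analysis without daily e-cigarette users as a sensitivity analysis.

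The daily-smoking variable should not be recoded for subjects already enrolled. It was used to match the groups, and changing it afterwards could undo that balance.

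The cost is a short amendment to Sections 7 and 11, one added screening item and one extra analysis. Some dual users become ineligible, which slows recruitment by an amount the documents do not allow one to estimate. Section 11.E discharges subjects for non-compliance, so the amendment should also say whether a plasma nicotine flag affects only the analysis or also continued participation.
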